**Principal Investigator:**

[name]

Dept of Nuclear Medicine,

Tata Memorial Hospital, Parel, Mumbai

**1. Introduction:** Targeted radionuclide therapy (TRT) is a nuclear medicine technique that uses radiopharmaceuticals (RPs) with high affinity to receptors or antigens on the surface of tumor cells to achieve a therapeutic effect. TRT causes less collateral damage than external beam radiotherapy (EBRT) because the RPs are selectively taken up by tumors and their metastases, delivering high doses of radiation to cancer cells and minimizing doses to normal tissues.(1) NETTER-1 and 2 trials have already established PRRT (Peptide Receptor Radionuclide Therapy) with Lutetium-177 (Lu-177) DOTATATE as first line TRT in metastatic well-differentiated gastro-enteropancreatic neuroendocrine tumors(GEP-NETs).(2,3). At Tata Memorial Hospital, we are routinely treating patients with PRRT with Lu-177 DOTATATE since 2019 and have completed nearly 700 cycles of PRRT till date.

While Lu-177 as a radioisotope is safe and indigenously produced by BARC, the recent global shortage of this isotope has led to development of Terbium-161 (Tb-161). Terbium-161 belongs to the same family of Lanthanides as Lu-177 and offers the same physical characteristics. (Table below)

Characteristics	Lutetium-177	Terbium-161
Half Life	6.7 days	6.9 days
Beta energy	134 keV	154 keV

**Advantage of using Tb-161 over Lu-177:** The superiority of Tb-161 over Lu-177 evolves from its basic property of emission of Auger electrons (AE).(4) Most important characteristics of radioisotopes in Nuclear Medicine or Radiation Oncology are linear energy transfer and range; which are determinants of cell-damage to the target cell and normal cell, respectively. Compared to beta-emissions (as in Lu-177), AEs are most lethal to cancer cells when emitted near the cell nucleus and especially when incorporated into DNA. AEs cause DNA damage both directly and indirectly via water

radiolysis. AEs can also kill targeted cancer cells by damaging the cell membrane and producing more targeted and lethal effects. Moreover, the important point is that since the range of delivery of this energy is relatively shorter as compared to beta-emitters, hence there is negligible bystander and crossfire effect, thereby causing no damage to surrounding cells.

**Monte-Carlo simulations:** Larauze et al assessed absorbed doses from simulations performed with CELLDOS, (5)(6) which is a homemade Monte Carlo track-structure code for simulating the transport of electrons in water, based on differential and total interaction cross sections describing the elastic scattering, electronic excitation, and ionization. Absorbed doses to cell nuclei and cell membranes (with an intranuclear radionuclide location, only nuclear absorbed doses were assessed) were assessed. In this tumor cluster model, when all cells were targeted, and depending on the location of the radionuclide, Tb-161 delivered a 2- to 3-fold higher nuclear absorbed doses than Lu-11 but also 2- to 6-fold higher absorbed doses to cell membranes. Interaction of ionizing radiation with the cell membrane induces sphingomyelin hydrolysis to ceramide, initiating apoptosis. Since a number of radiopharmaceuticals reside on the membrane without being internalized (e.g., neuropeptide antagonist analogs and many antibodies), understanding the role of the cell membrane as a target becomes particularly important, specifically for TRT. ***With the radionuclide at the cell surface, absorbed doses to cell membranes were higher than nuclear doses, both with Lu-11 (7.4-fold higher: 38–41 vs. 4.7–7.2 Gy) and with Tb-161 (22-fold higher: 237–244 vs. 9.8–15.1 Gy).***

**Cell survival studies:** Spoormans et al performed cellular dosimetry to quantify the absorbed dose to the cell nucleus and compared dose–response curves to evaluate differences in relative biological effectiveness in vitro, between Tb-161 and Lu-177. (7) Tb-161-DOTATATE and delivered a 3.6 times higher dose to the nucleus, respectively, than their Lu-177-labeled counterparts on saturated receptor binding. This increased

nucleus-absorbed dose was mainly due to the additional emission of internal conversion electrons by Tb-161. When activity concentrations were considered, both Tb-161-DOTATATE showed a lower survival fraction than did labeling with Lu-177. When the absorbed dose to the nucleus was considered, no significant difference could be observed between the dose-response curves for Tb-161- and Lu-177-DOTATATE. Tb-161-DOTATATE showed only a linear dose response within the observed dose range, suggesting additional cell membrane damage by Auger electrons.

**Tb-161 dosimetry:** Verberg et al did a comparative dosimetric analysis of Lu-177 DOTATATE and Tb-161 DOTATATE by calculating the radiation absorbed dose to tumor as well as non-target organs of normal biodistribution, on adult human phantom models.(8) The substitution of Lu-177 with Tb-161 results in an increase in the delivered dose per unit of activity to tumour tissue by 40% (in a 10 g tumour: 2.9 Gy/GBq and 4.1 Gy/GBq, respectively) as well as to dose-limiting non-target tissue (kidneys: 39%(0.73 Gy/GBq and 1.01 Gy/GBq, respectively), bone marrow: 42% (0.04 Gy/GBq and 0.06 Gy/GBq, respectively)). If an equivalent non-target delivered dose is strived for in order not to increase toxicity, the registered standard activity of 7400 MBq [200 mCi]Lu-177-DOTATATE per therapy cycle should be replaced with a standard activity of 5400 MBq [145 mCi] Tb-161 DOTATATE.

**First-In-Human Studies:** After qualifying through the cell survival and dosimetry studies, Baum et al used Tb-161 DOTATATE in 2 patients, one with paraganglioma and other with metastatic neuroendocrine tumor, both of whom were refractory to Lu-177 DOTATATE therapy.(9) Patients formally consent to receive this treatment and Tb-161 DOTATATE was administered following the standard PRRT protocol. Post therapy SPECT/CT images were acquired which showed tracer localisation at the desired tumor locations. No adverse events and no changes in vital parameters were observed or reported by the patient during, immediately after or at follow-up review of the patient

after administration of Tb-161-DOTATATE. According to the Common Terminology Criteria for Adverse Events, there were no clinically significant changes in the relevant laboratory values (hematological, renal, and hepatic panel) at the subsequent follow up of the patient after administration of Tb-161-DOTATATE.

**Current global trials of Tb-161 labeled radionuclide therapy:**

VIOLET is an investigator-initiated, single-centre, phase 1/2 trial, conducted at the Peter MacCallum Cancer Centre (Melbourne, VIC, Australia), with progressive metastatic prostate cancer treated with Terbium-161 PSMA. It is important to note that the toxicity is primarily caused by radioisotope (Tb-161) and not due to ligand (PSMA), in our case DOTATATE. The initial results published (10) show that grade 3 treatment-related adverse events (TRAEs) were limited to pain (one [3%] of 30; the only serious TRAE) and lymphopenia (one [3%] of 30). No grade 4 TRAEs or treatment-related deaths occurred. No dose reductions or treatment discontinuation occurred for toxicity.

**Current Indian scenario:** As of today, Tb-161 DOTATATE is already commercially available in India and first therapy has already been administered, with multiple centers now starting this treatment. Dept of Nuclear Medicine, TMH and ACTREC has already obtained approval from Atomic Energy Regulatory Board (AERB), and has treated 2 patients of metastatic NET on compassionate basis with Tb-161 DOTATATE, who were refractory to Lu-177 DOTATATE.

We therefore would like to study the safety and efficacy of Tb-161 DOTATATE in patients in metastatic NET who have shown disease progression after treatment with Lu-177 DOTATATE PRRT.

**2. Aims and Objectives:**

**Aim:** To evaluate the safety and efficacy of Terbium 161 DOTATATE PRRT in metastatic neuroendocrine tumors who have progressed on Lu-177 DOTATATE PRRT.

**Objectives:****Primary:**

- To determine disease control rate in metastatic neuroendocrine tumors who have progressed on Lu-177 DOTATATE PRRT.

**Secondary:**

- To assess the safety profile expressed in terms of incidence of >grade 3 toxicity or proportion of patients developing > grade 3 in metastatic neuroendocrine tumors who have progressed on Lu-177 DOTATATE PRRT.

**3. Study End-point:** Safety and efficacy assessment**4. Study Design:** Phase II (Simon Two Stage), Interventional, Single Arm, Open Label**5. Study Sites:** Departments of Nuclear Medicine, TMH, Parel and RRU, ACTREC**6. Pre-screening:** Patients of metastatic NET who have progressed on Lu-177

DOTATATE PRRT will be referred after discussion in Neuroendocrine Tumor Clinic, TMH or HPB-UGI Clinic at RRU, ACTREC.

**7. Screening:** Patients will be confirmed for disease progression on Ga-68 DOTATATE and/or FDG PET/CT imaging.**8. Inclusion Criteria:**

- Male or female, age greater than 18 years
- Histopathological diagnosis of well-differentiated GEP-NET
- Positive Ga-68-DOTANOC PET/CT, Krennigs score  $\geq 3$
- Locally advanced/inoperable disease or metastatic disease
- Patient who have shown disease progression with Lu-177 DOTATATE PRRT

- Karnofsky performance-status score of at least 60 or ECOG performance status </=2
- Life expectancy greater than 6 months

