#### **9. Exclusion criteria**

- Serum creatinine level of more than 1.6 mg/dl or a creatinine clearance of less than 50 ml/min
- Hemoglobin level of less than 8.0 g per deciliter
- Red blood cell count less than 300,000/cubic millimeter
- White cell count of less than 2000 per cubic millimeter
- Platelet count of less than 75,000 per cubic millimetre
- Total bilirubin level of more than 3 times the upper limit of the normal range
- Serum albumin level > 3.0 g/dl
- Pregnancy and Lactation
- Patients with concurrent malignancies

**10. Study Methodology:** Patients referred from Neuroendocrine tumor clinic fulfilling the inclusion and exclusion criteria will be enrolled in the study for treatment with Terbium-161 DOTATATE. Since the physical characteristics of Tb-161 are same as Lu-177 and since the peptide is same (DOTATATE), principles and procedure of treatment is same as Lu-177 DOTATATE PRRT. This is a day care therapy and the patient shall be admitted and discharged on the same day. Patients will be administered 2 cycles of Tb-161 PRRT at intervals of 8-12 weeks. Pre-therapy investigations will be as per 'standard of care' work-up for PRRT. Even the therapy administration protocol will be same, which will be as follows:

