**15. Study Assessments:**

**Response assessment:** Disease control rate will be measured as a primary endpoint. It is percentage of patients achieving complete or partial response or stable disease on Ga-68 DOTATATE PET/CT. Response assessment will be done using RECIST 1.1 for solid tumors. Non-PD (non-disease progression) after one session of Tb-161 therapy will be eligible for the second session. Patients showing CR with no

residual measurable disease will not undergo a second session of therapy. Patients with PD after 1 cycle of Tb-161 DOTATATE therapy will not continue in the study and will be referred to NET Clinic for further management. Currently there is no standard of care for treatment of refractory NET.

**Safety Assessment:** At each visit, the investigator will evaluate the subject to determine whether any AEs have occurred. CBC, LFT, RFT, Serum electrolytes will be done at 2 weeks, 4 weeks and 6 weeks after each therapy. AEs may be directly observed, reported spontaneously by the subject or by questioning the subject at each study visit. All laboratory values will be evaluated by the Investigator as to clinical significance. All post-baseline abnormal laboratory values considered clinically significant by the Investigator will be recorded as an AE. The NCI Common Terminology Criteria for Adverse Events version 5 (NCI CTCAE v5.0) will be used to classify and grade the intensity of adverse events during and after each treatment cycle. CTCAE will be used to grade all events regardless of attribution, in order to ensure objective reporting, and in order to report trial data according to accepted international guidelines. The highest grade of each observed toxicity will be recorded. The results will be computed in a tabular form in which the proportion of people having their highest grade of toxicity will be charted.

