**AEs are not required to be reported unless they meet SAE criteria.**

Adverse events for Terbium are expected to be nausea (30-40%), vomiting (25-30%). Other common adverse events may include fatigue or asthenia and diarrhoea. Grade 3 or 4 neutropenia, thrombocytopenia, and lymphopenia may be seen in 1%, 2%, and 9% of patients respectively.

**Adverse event management:** All adverse events will be managed as per institutional standards in concordance with gastrointestinal disease management group.

**SAE reporting:** All SAE will be reported within 24 working hours to the IEC, follow up will be given within 14 days and a final SAE will be submitted at resolution of the SAE.

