#### **16. Statistical Analysis for sample size calculation:**

At the end of the study, we expect a disease control rate (DCR) of 87% in patients with metastatic NET progressed after Lu-177 DOTATATE PRRT.

Baseline assumption is DCR of 67% from historic control and addition of Terbium-161 DOTATATE therapy will improve DCR by 20%. The null hypothesis will be tested against a one-sided alternative with type I error rate of 0.05 & power of 0.80 in standard Simon two stage design. In the first stage, 6 patients will be accrued. If there are <4 responses, the study will be stopped. Otherwise, 14 additional patients will be accrued for a total of 20. The null hypothesis will be rejected if =/≥ 16 responses are observed in 20 patients.

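### The only listed secondary objective sets its safety threshold strictly above grade 3, so read literally its headline toxicity figure leaves out grade 3 events

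*Protocol*

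**What the plan says.** Section 2 lists one secondary objective, safety, to be expressed as "incidence of >grade 3 toxicity or proportion of patients developing > grade 3". The strict sign appears twice, with no equals sign in the text as read.

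The other places that bear on the threshold are these:

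- Section 3 (Study End-point) gives only "Safety and efficacy assessment", with no grade and no measure.
- Section 15 (Safety Assessment) grades events by CTCAE v5.0, whatever their cause, and records the worst grade of each toxicity. It then plans a table: "The results will be computed in a tabular form in which the proportion of people having their highest grade of toxicity will be charted". It sets no threshold and does not refer back to the objective.
- Section 15 (expected adverse events) states: "Grade 3 or 4 neutropenia, thrombocytopenia, and lymphopenia may be seen in 1%, 2%, and 9% of patients respectively".
- Section 1 (current global trials) reports from a 30-patient Tb-161 trial in prostate cancer that "grade 3 treatment-related adverse events (TRAEs) were limited to pain (one [3%] of 30; the only serious TRAE) and lymphopenia (one [3%] of 30", and then: "No grade 4 TRAEs or treatment-related deaths occurred".

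**The concern.** A limit strictly above grade 3 selects grades 4 and 5. Where the protocol discusses the more serious toxicities elsewhere, grade 3 is included: in the expected rates of section 15 and in the trial it cites for the safety of Tb-161. A measure confined to grades 4 and 5 cannot be set against either of them.

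The objective carries the safety half of the trial's aim. If it were followed as written, the headline result could be zero while the table of highest grades in the same report showed grade 3 events. A reader who saw only the headline would take the treatment to be better tolerated than the table shows.

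**Working it through.** The protocol derives no figure from this threshold, so there is none to reproduce. The check is a comparison of texts, followed by two illustrations of size.

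**1. Is the limit made inclusive anywhere?** Section 3 gives no grade. The Safety Assessment in section 15 gives a scale and a table but no limit. The expected rates in section 15 combine grades 3 and 4 but do not define the objective. Section 1 describes another trial. Nothing overrides the strict sign in section 2. Nor does any section say outright that grade 3 was meant to count, so that remains an inference, though a strong one.

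**2. The threshold applied to the cited trial.** Inputs from section 1: 30 patients, one grade 3 pain event, one grade 3 lymphopenia, no grade 4 treatment-related event and no treatment-related death. The protocol does not say whether the two grade 3 events were in one patient or two, so both cases are shown. Intervals are exact (Clopper-Pearson) 95%. For zero events the upper limit is 1 − 0.025^(1/30) = 0.116.

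| Threshold | Patients counted | Proportion | Exact 95% CI |
|---|---|---|---|
| Above grade 3 (as written) | 0/30 | 0% | 0 to 11.6% |
| Grade 3 or higher, both events in one patient | 1/30 | 3.3% | 0.1 to 17.2% |
| Grade 3 or higher, events in two patients | 2/30 | 6.7% | 0.8 to 22.1% |

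The written threshold removes every treatment-related event of grade 3 or above that the protocol reports from that trial.

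**3. The protocol's own expected rates.** Inputs: rates of 1%, 2% and 9% for grades 3 and 4 together (section 15) and a maximum of 20 patients (section 16). With grade 3 counted, the expected number is 20p and the chance of at least one affected patient is 1 − (1 − p)^20.

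| Toxicity | p | Expected of 20 | Chance of at least one |
|---|---|---|---|
| Neutropenia | 0.01 | 0.2 | 18.2% |
| Thrombocytopenia | 0.02 | 0.4 | 33.2% |
| Lymphopenia | 0.09 | 1.8 | 1 − 0.91^20 = 84.8% |

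Section 16 also allows an early stop: "In the first stage, 6 patients will be accrued. If there are <4 responses, the study will be stopped". With 6 patients the lymphopenia figures are 6 × 0.09 = 0.54 expected and 1 − 0.91^6 = 43.2%.

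Under the strict threshold only the grade 4 part of these rates would count. The protocol does not give that part. For lymphopenia in 20 patients the expected count therefore lies anywhere from 0 (all cases grade 3) to 1.8 (all cases grade 4), and the document does not allow it to be narrowed.

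**The case against.** **The sign may be an artefact.** An underlined sign in the source could have lost its underline when the PDF was read. Inclusive signs do survive elsewhere: in the inclusion criteria (section 8) and in the rejection rule (section 16). Those are typed characters, however, and their survival does not show that an underline would survive. This objection stands in part: the artefact is neither shown nor excluded, which is why the source file must be checked first.

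**Grade 3 events are not lost.** A reader might infer that they would go unrecorded, or that the objective is the only safety measure. The protocol supports neither. The highest-grade table in section 15 is a second safety summary, in which grade 3 would be visible. This objection stands, and it confines the problem to the headline measure.

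**Incidence or proportion.** A reader might also infer that the objective leaves two different measures open, because section 10 plans repeated treatment ("Patients will be administered 2 cycles of Tb-161 PRRT at intervals of 8-12 weeks") and events could then outnumber patients. The documents do not support this as an error. Incidence of toxicity is commonly used for the share of patients affected, so the two terms can be synonyms. Section 15 counts people by highest grade, and no section plans an event rate or a per-cycle denominator.

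**The cited trial is only an illustration.** It used another ligand in another disease, and the figures are for treatment-related events, whereas section 15 grades events of any cause. This is correct. The trial shows how the threshold acts; it does not predict the rate in this study.

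**Conclusion.** The point holds as a minor wording error in one sentence. As written, the threshold of the only listed secondary objective counts grades 4 and 5 only, which is out of step with the protocol's own expected rates and with the trial it cites. In that trial the effect is 0/30 instead of 1/30 or 2/30. Here, for lymphopenia alone in 20 patients, including grade 3 gives 1.8 expected cases at the protocol's rate, against an undetermined number between 0 and 1.8 as written. These figures assume that all 20 patients are treated and that the 9% rate applies; they cover one toxicity and not all toxicity.

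It would go too far to say how likely a headline of zero is. That depends on the share of cases reaching grade 4, which the protocol does not state. The primary endpoint, sample size, Simon decision rule, data capture and grading are all unaffected. Confidence is medium, because a lost underline cannot be ruled out from this text.

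**What to change.** 1. Check the source file for an underline beneath the sign in the secondary objective.
2. Whatever the check shows, state the threshold in words so that it cannot be lost again: *the proportion of treated patients with at least one toxicity of grade 3 or higher (CTCAE v5.0)*. Counting patients agrees with the table in section 15. If grades 4 and 5 only are really intended, say that in words instead.
3. Keep the highest-grade table, broken down by toxicity, so that results can be compared with the 1%, 2% and 9% expected rates.

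The cost is one reworded sentence, with no new visits, tests or patients. The reported toxicity rate may be higher than under the strict threshold, because grade 3 events are then counted.

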#### **9. Exclusion criteria**

- Serum creatinine level of more than 1.6 mg/dl or a creatinine clearance of less than 50 ml/min
- Hemoglobin level of less than 8.0 g per deciliter
- Red blood cell count less than 300,000/cubic millimeter
- White cell count of less than 2000 per cubic millimeter
- Platelet count of less than 75,000 per cubic millimetre
- Total bilirubin level of more than 3 times the upper limit of the normal range
- Serum albumin level > 3.0 g/dl
- Pregnancy and Lactation
- Patients with concurrent malignancies

**10. Study Methodology:** Patients referred from Neuroendocrine tumor clinic fulfilling the inclusion and exclusion criteria will be enrolled in the study for treatment with Terbium-161 DOTATATE. Since the physical characteristics of Tb-161 are same as Lu-177 and since the peptide is same (DOTATATE), principles and procedure of treatment is same as Lu-177 DOTATATE PRRT. This is a day care therapy and the patient shall be admitted and discharged on the same day. Patients will be administered 2 cycles of Tb-161 PRRT at intervals of 8-12 weeks. Pre-therapy investigations will be as per 'standard of care' work-up for PRRT. Even the therapy administration protocol will be same, which will be as follows:

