**20. Informed consent:** The Investigator or a person designated by him/her will collect informed consent from all participants, prior to which the Investigator or co-investigator must inform each participant of the objectives, benefits, risks and requirements of the study. He/she will also provide the participant with an information sheet in clear, simple language. The study participant will be allowed ample time to inquire about details of the study and to decide whether or not to participate in the study. Moreover, the patient will receive a written "patient information", containing all relevant information for the patient's decision and the course of the study. The consent of the patient to participate must be obtained in writing before recruitment into the study. The informed consent form must be dated and signed by the patient. Thereby, he declares his voluntary consent to participate in the study and his willingness to comply with the requirements of the trial and the instructions of the treating investigator during the course of the study. There are two copies of the informed consent form: one for the patient and one to be kept by the investigator in his study documents. The informed consent is only valid after receiving the patient's signature. Thereafter, the patient can be entered into the study if he/she fulfills the selection criteria. The study will not commence until approval has been obtained from the Tata Memorial Hospital Human Ethics Committee.

**21. Protocol amendments:** Any modifications to the protocol which may impact on the conduct of the study, potential benefit of the study, or may affect patient safety, including changes of study objectives, study design, patient population, sample sizes, study procedures, or significant administrative aspects will require a formal amendment to the protocol. Such amendment will be agreed upon by the investigators and then submitted to the IEC/IRB for acceptance.

Administrative or technical changes of the protocol such as minor corrections and/or clarifications that have no effect on the way the study is to be conducted, nor on the risk-benefit ratio, will be agreed upon by all the investigators and will be documented in a memorandum to the protocol. The IEC may be notified of such changes at the discretion of the sponsor/coordinating investigator. The coordinating investigator has to assure, that all amendments have been added to the study documents at any site involved in the trial.

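### The albumin exclusion line is reversed: as written it bars every patient with albumin above 3.0 g/dl, and nothing in the protocol corrects it

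*Protocol*

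**What the plan says.** The exclusion list in section 9 of the protocol contains "Serum albumin level > 3.0 g/dl". It stands beside six other laboratory lines, for example "Hemoglobin level of less than 8.0 g per deciliter" and "Total bilirubin level of more than 3 times the upper limit of the normal range".

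The list is operative. Section 10 says that referred patients "fulfilling the inclusion and exclusion criteria will be enrolled in the study for treatment with Terbium-161 DOTATATE", and section 20 says that after consent "the patient can be entered into the study if he/she fulfills the selection criteria".

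Section 5 names the sites as "Departments of Nuclear Medicine, TMH, Parel and RRU, ACTREC". Section 16 plans a first stage of 6 patients and then: "Otherwise, 14 additional patients will be accrued for a total of 20".

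**The concern.** A patient who meets a line in an exclusion list cannot enter. The albumin line therefore admits patients at or below 3.0 g/dl and turns away everyone above. Low albumin is generally taken as the sign of impaired function or poor general condition; that is general laboratory knowledge, not something the protocol states. On that footing the line works against the rest of the list. It also works against the inclusion criteria in section 8, which ask for a minimum performance status and a life expectancy of more than six months.

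At stake is which population the trial treats. Staff must either follow a rule that was probably not meant or override a written eligibility rule. The first gives a low-albumin cohort. The second gives a cohort in which most or all patients may be recorded as ineligible.

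**Working it through.** No sample-size or error-rate figure enters this point. The check is a classification of the lines, a search of the document, and a comparison of the eligible sets.

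**Step 1. Which side each laboratory line in section 9 excludes**

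| Line | Excluded values | Side excluded |
|---|---|---|
| Creatinine / creatinine clearance | above 1.6 mg/dl / below 50 ml/min | impaired |
| Haemoglobin | below 8.0 g/dl | impaired |
| Red cells | below 300,000/mm³ | impaired |
| White cells | below 2000/mm³ | impaired |
| Platelets | below 75,000/mm³ | impaired |
| Total bilirubin | above 3 times the upper limit of normal | impaired |
| Albumin | above 3.0 g/dl | preserved |

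Six of seven lines exclude the impaired side and one excludes the preserved side. The contrast lies in the side of function, not in the bare sign: creatinine and bilirubin also exclude values above a limit. Albumin is also the only laboratory line that uses a symbol; the others put the comparison in words. That fits a slip, or a line moved from an inclusion list.

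**Step 2. Whether another place corrects it**

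Albumin occurs once in the protocol. The inclusion criteria in section 8 have no albumin line. Sections 12 and 15 mention liver function tests only as follow-up investigations, without a threshold. Nothing overrides section 9.

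**Step 3. Eligible sets under each reading**

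- Literal: albumin ≤ 3.0 g/dl.
- Sign reversed (exclude below 3.0): albumin ≥ 3.0 g/dl.
- Misplaced inclusion criterion (include above 3.0): albumin > 3.0 g/dl.

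The literal set shares only the single value 3.0 g/dl with the second set, and nothing with the third.

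**Step 4. Consequence for the planned 20 patients**

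If sites apply either repaired reading while the text stays as it is, each patient above 3.0 g/dl is a deviation from a written criterion: up to 20 of 20, or up to 6 of 6 at the first stage.

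If sites apply the literal reading, let p be the share of otherwise eligible patients above 3.0 g/dl. Filling 20 places then needs about 20/(1 − p) otherwise eligible patients. The protocol gives no value for p, so these are assumed values, for illustration only:

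| Assumed p | 20/(1 − p) |
|---|---|
| 25% | 20/0.75 = 27 |
| 50% | 20/0.50 = 40 |
| 75% | 20/0.25 = 80 |
| 90% | 20/0.10 = 200 |

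These figures assume that the trial goes on to its full size rather than stopping after the first 6 patients.

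**The case against.** The strongest reply is that any clinician would see what was meant. On the intended reading, this line does not by itself bias the disease control rate, and no endpoint, error rate or decision rule changes. What remains is a documentation problem. This is right about the primary result under that reading. It does not remove the defect, because it concedes the error and leaves staff to override a written entry rule patient by patient.

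Other points on that side:

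- **Misread sign.** The text was extracted from a PDF, so a misread sign cannot be wholly excluded. Nothing specific suggests one, and the same symbol reads normally elsewhere in the protocol.
- **Illustrative figures.** The screening numbers rest on assumed shares and apply only to the literal reading. This stands: they show scale and are not evidence.
- **Two sites.** Nothing shows that the two sites would read the line differently. This stands too. The correction is needed with one site or two; a second site only adds a chance of inconsistency.
- **Lighter route.** Section 21 also allows a memorandum for minor corrections that do not affect conduct. A sponsor could argue for it, but the correction almost wholly replaces the written eligible population on this criterion. Section 21 says that changes of "patient population, sample sizes, study procedures, or significant administrative aspects will require a formal amendment to the protocol".

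**Conclusion.** The point holds and must be fixed before enrolment. One of seven laboratory exclusion lines is reversed in effect, and the protocol offers no correction. As written, every patient above 3.0 g/dl is barred. If the presumed intent is applied instead, up to all 20 planned patients breach a written criterion.

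The conclusion rests on the wording of section 9, on albumin appearing nowhere else, and on the general understanding that low rather than high albumin marks impairment. The share of patients affected is unknown. No effect on the disease control rate is claimed under the intended reading. The case for correction is that the text governs who may be treated.

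**What to change.** Before enrolment, the sponsor should reconcile the direction or placement of the albumin line with the rest of section 9. The clinical team should confirm the cut-off; no value or direction is proposed here. A reversed sign and a misplaced inclusion criterion treat a patient at exactly 3.0 g/dl differently, so the new text must say which applies.

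The change should go to the ethics committee as a formal amendment under section 21. Any screening form or case record form page that repeats the line should be corrected at the same time. If patients have already been enrolled or refused, their albumin values should be checked against the old and the new text and the result documented.

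The cost is one amended eligibility line and the matching forms, with no extra patients, visits or procedures.
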